13. SAMPLE SIZE AND STATISTICAL ANALYSIS

Primary outcome

One year all-cause mortality will be compared between randomised groups using a Mantel-Haenszel Chi-square test, stratified by study centre. A two-tailed p-value <0.049 will be taken to indicate statistical significance.

Power analysis

One year all-cause mortality is expected to be ~10% based on the findings of Leslie et al's study and Australasian studies [9,25]. The reduction in mortality in the light anaesthesia group is expected to be 20%. A power analysis using p1=0.10 and p2=0.08 indicates that N=3250 patients are required in each group, β =0.8, α =0.049. The alpha level is reduced to allow for the single interim analysis.

The primary and secondary outcomes will initially be analysed using the full analysis set population i.e. using those individuals who have confirmed outcomes. Sensitivity analyses will also be undertaken, as appropriate, for which those missing outcome data will be assigned a poor outcome. Complete listings, according to randomised group, will be compiled of those lost to follow-up, and include relevant explanations.

Secondary outcomes

The presence of MI, cardiac arrest, stroke, PE, sepsis, surgical site infection, awareness and persistent post-operative pain at 30 days and one year as appropriate will be compared between randomised groups using Mantel-Haenszel chi-square tests or Fisher's exact test depending on the expected cell frequencies. Additionally a composite score including the presence of any of MI, cardiac arrest, stroke and PE, will be compared between randomised groups also using a chi-square test.

Additional analyses will also explore the role of MI, cardiac arrest, stroke, PE, sepsis, surgical site infection and cancer recurrence on one year mortality using Cox's proportional hazards regression to develop a model of independent predictors of one year mortality. The randomised group will be added to this model to assist explanation of any observed differences in outcome between the randomised groups.

Secondary analyses will be undertaken on an intention to treat basis. The vast majority of participants will have assessments of the primary outcome (one-year mortality) and the 30-day secondary outcomes. Permission will be sought as necessary to extract these from national databases and local hospital records.

Adverse events

The adverse event rates for non-outcome variables will be summarised for each randomised group as percentage of patients and as frequencies (number of occurrences) and compared between groups using Chi-square, Fisher's exact and Poisson regression depending on incidence rates.

Interim Analysis

The interim analysis of the primary outcome for efficacy and futility will be undertaken when 2000 participants have completed the one-year follow-up, which is likely to be after two years' recruitment. The p-value for this analysis is set at p<0.001 and the primary analysis p-value is adjusted accordingly to 0.049, to preserve the type I error rate. The analysis will be undertaken on the intention-to-treat (ITT) population, with all randomised participants included and analysed according to randomised treatment, irrespective of actual treatment.

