been published using available databases. Five of these have found similar increases in mortality. In Lindholm et al.'s study, deep hypnotic time was not a predictor when pre-existing malignancy was included in the model. If deep hypnotic time was >2 hours subsequent mortality was much higher. Searleman et al.'s study found that non-surviving patients received slightly less volatile anaesthetic than the survivors, implying that patients who died may have been sensitive to the anaesthetic drugs. Saager et al.'s study used a very large database with 24,000 patients, and found three independent predictors of increased one year mortality, which were minimum alveolar concentration (MAC) <0.4, mean arterial pressure (MAP) <80 mmHg and BIS<40. (MAC is a normalised measure of anaesthetic potency). The risk to those who received deep anaesthesia was again a 20% increase in one-year mortality. Patients with a low MAP during the procedure faired even worse, and the combination of all three factors was associated with a RR=1.6 for one year mortality. They also found that patients who had an instance of low MAP, which was treated within 5 minutes had improved outcomes, indicating that although patients who were sensitive to anesthesia did poorly, early intervention was effective. Leslie et al analysed long-term outcomes in the B-Aware Trial, a 2,500 patient trial conducted principally in New Zealand, Australia and Hong Kong. This study also found an increased risk of myocardial infarction and cerebrovascular accident in the deep anaesthesia group. There were a large number of cardiac patients in the study and the same relationship of depth with poor outcome was confirmed, a finding repeated by Kertai et al. [17].

Author	Ν	ASA	1 y	Increased risk of
		3&4 *	mortality	death if 'deep' [#]
Monk 2005 [12]	1064	35%	5.5	RR = 1.24
Lindholm 2009 [13]	4087	6%	4.3	HR = 1.18
Saager 2009 [14]	23,999	~30%	4.8	RR = 1.63
Searleman 2010 [15]	1791	71%	10.7	OR = 1.25/h
Leslie 2010 [16]	2463	74%	10.8	PS = 1.42 (at 4y)
Kertai 2010 (cardiac) [17]	460	100%	17.8	HR = 1.29 (at 3y)
Kertai 2011 (non-cardiac) [18]	1473	60%	24.3	HR = 1.03 (at 3y)

TABLE 1 Observational studies of the relationship between depth of anaesthesia and subsequent mortality

*ASA=American Society of Anaesthesiologists physical status scale, 1=normal health, 2=mild to moderate systemic disturbance, 3=severe systemic disturbance which limits activity, 4=incapacitating life threatening disease, 5=moribund.

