Anaesthesia will consist of standard anaesthetic hypnotics, volatiles, opioids and relaxants, intravenous or inhalational induction, volatile maintenance, opioids and muscle relaxants, with continuous BIS monitoring. No use of nitrous oxide will be allowed due to its interference with accurate BIS readings and similarly no infusions of ketamine above 25 mg/h will be allowed.

An individualised mean arterial blood pressure target range appropriate for the patient being studied will be set by the anaesthetist before BIS target randomisation. Anaesthetists will be encouraged to maintain patient normothermia and to give DVT prophylaxis and antibiotic prophylaxis as per local institutional practice. Other aspects of anaesthesia and perioperative care will be at the discretion of the anaesthetist. All complications (including those defined as secondary outcomes) will be managed according to routine institutional practice.

Recordings

Data will be collected by interviewing patients, relatives and doctors, and by review of hospital medical records and national databases (if applicable). Source documentation may be requested for any or all data recorded. Any or all data recorded may be subject to assessment by the Endpoint Adjudication Committee (on the direction of the Steering Committee).

Pre-operative

Age, sex, height, weight, ASA physical status, electrocardiogram (ECG), haemoglobin, creatinine, albumin, updated Charlson co-morbidity score [57,63], WHODAS-12 score

Intra-operative

Electronic *or* printed record with minimum of 5 minutely recording of BIS, burst suppression ratio (SR), end-tidal volatile anaesthetic concentration, mean arterial blood pressure and heart rate.

Manual record of all drugs used, including total dose of opioids used and regional or local anaesthetic blocks used.

Recovery

Analgesic and antiemetic requirements, time of arrival and eligibility for discharge.

Post-operative days 1, 2, 3

Routine laboratory testing.

Incidence of MI, cardiac arrest, PE, stroke, sepsis, surgical site infection and other adverse events.

Questioning for evidence of awareness under anaesthesia using the modified Brice questionnaire administered once, preferably on the day following surgery.

Analgesic and antiemetic requirements.

Quality of recovery: A validated post-operative quality of recovery score, the QoR-15 score will be recorded [58].

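### The primary mortality test is valid and has its stated power, but it adjusts for centre only; using baseline predictors already recorded would add about 1 to 5 points of power at no cost in patients

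*Protocol*

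**What the plan says.** Protocol section 13, Primary outcome, names one comparison: "One year all-cause mortality will be compared between randomised groups using a Mantel-Haenszel Chi-square test, stratified by study centre". The threshold follows: "A two-tailed p-value <0.049 will be taken to indicate statistical significance". Centre is also the only factor used to stratify randomisation (section 10, Treatment allocation), so the test matches the allocation scheme.

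The sample size is that of an unadjusted comparison of two proportions: "A power analysis using p1=0.10 and p2=0.08 indicates that N=3250 patients are required in each group", with "β =0.8, α =0.049". The 0.8 is evidently the power.

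The pre-operative recordings in section 10 are "Age, sex, height, weight, ASA physical status, electrocardiogram (ECG), haemoglobin, creatinine, albumin, updated Charlson co-morbidity score", followed by the 12-item WHODAS score.

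The one regression for mortality in section 13 is a Cox model built on myocardial infarction, cardiac arrest, stroke, pulmonary embolism, sepsis, wound infection and cancer recurrence, with randomised group added to help explain differences. Those are all events after randomisation, so this model does not give a baseline-adjusted treatment effect.

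**The concern.** For a binary outcome in a randomised trial, adjusting for baseline variables that predict the outcome usually makes the treatment comparison more precise, and the gain grows with the strength of prediction. This protocol collects plausible predictors of one-year death in every patient but leaves them out of the primary comparison.

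The protocol settles the primary test itself, so the point concerns a choice it has made and not a detail left to an SAP. What is at stake is a few points of power in a design with little margin: 3,250 planned per arm against 3,233 needed, a surplus of 17 per arm.

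**Working it through.** **Inputs from the protocol (section 13).** Mortality 10% (deep) and 8% (light), two-sided alpha 0.049, power 80%, 3,250 per arm.

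**Input not in the protocol.** The prognostic strength of the baseline variables. It is assumed below and shown as a range.

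**Step 1: reproduce the stated size.** Pooled two-proportion formula, no continuity correction, with mean risk 0.09:

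n = [z(α/2)·√(2·0.09·0.91) + z(β)·√(0.10·0.90 + 0.08·0.92)]² / 0.02²

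- z(α/2) = 1.9686 for alpha 0.049, so the first term is 0.7967.
- z(β) = 0.8416, so the second term is 0.3404.
- n = (1.1371 / 0.02)² ≈ 3,233 per arm, 0.5% below the stated 3,250.

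Power at 3,250: (0.02·√3250 − 0.7967) / √(0.10·0.90 + 0.08·0.92) = (1.1402 − 0.7967) / 0.4045 = 0.849, and Φ(0.849) = 80.2%. The plan delivers the power it claims.

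**Step 2: effect of adjustment.** To a good approximation, adjustment multiplies the variance of the marginal risk difference by 1 − R², where R² is the share of outcome variance explained by baseline risk. The effective size is then 3250 / (1 − R²) per arm. R² comes from a normally distributed baseline score on the log-odds scale, with average risk set to 9%.

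| SD of score (log-odds) | C-statistic (assumed) | R² | Effective n per arm | Equivalent extra patients, both arms | Power |
|---|---|---|---|---|---|
| none | – | 0 | 3,250 | 0 | 80.2% |
| 0.50 | 0.64 | 0.021 | 3,320 | about 140 | 81.0% |
| 0.75 | 0.70 | 0.049 | 3,416 | about 330 | 82.1% |
| 1.00 | 0.75 | 0.086 | 3,557 | about 610 | 83.6% |
| 1.25 | 0.80 | 0.131 | 3,742 | about 980 | 85.4% |

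**Step 3: check by simulation.** 1,500 trials per scenario, 3,250 per arm, risks of 10% and 8%, comparing an unadjusted chi-square test with logistic regression on one baseline score:

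| C-statistic | Unadjusted power | Adjusted power |
|---|---|---|
| 0.63 | 78.6% | 78.9% |
| 0.71 | 79.3% | 80.7% |
| 0.75 | 81.7% | 85.2% |
| 0.79 | 79.5% | 85.1% |

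Monte Carlo error is about 1 point. The gain is near zero for weak predictors and grows to about 6 points at 0.79, broadly in line with the analytic table.

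**Step 4: can the model be fitted?** Expected deaths are 3,250·0.10 + 3,250·0.08 = 585. With the 20 centres foreseen in section 14, the proposed model has 19 centre terms, one for group and four for covariates entered linearly, 24 in all. That is 585 / 24 ≈ 24 deaths per term.

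**The case against.** The strongest reply is that nothing here is wrong. The test is pre-specified, valid and matched to the stratified randomisation, and the sample size was computed for an unadjusted comparison and reproduces. The trial loses nothing relative to its own plan. All of that stands, so the point is offered as an improvement only.

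Second, the size of the gain rests on a C-statistic the protocol does not give. This also stands. Eligibility is limited to age 60 and over and ASA 3 or 4, which narrows the spread of two of the proposed covariates and makes the upper scenarios less secure.

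Third, a supportive adjusted analysis is commonly left to the SAP. That is right, and its absence from the protocol is not criticised. What remains is the choice of primary test, which the protocol does fix.

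Two stronger readings are tempting, and the protocol supports neither:

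- *That chance imbalance in comorbidity or cancer is left as an uncorrected flaw.* With 3,250 per arm, the standardised difference of any baseline variable has SD √(2/3250) ≈ 0.025, so 95% of such differences lie within about ±0.05 SD. The type I error of the unadjusted test already allows for them.
- *That the background names comorbidity and malignancy as the dominant causes of one-year death.* Section 9 says half the deaths in one cohort were due to cancer, that mortality there was 10.3% over age 65 against 5.5% overall, and that in another cohort "deep hypnotic time was not a predictor when pre-existing malignancy was included in the model". The last is confounding in observational data, which randomisation addresses. Together these make it plausible that baseline variables predict death, but they do not say how strongly.

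Finally, the thin margin should not be pressed too far. The protocol states no allowance for losses, but it expects primary outcomes to be nearly complete: "The vast majority of participants will have assessments of the primary outcome (one-year mortality) and the 30-day secondary outcomes". Adjustment is not a remedy for missing outcomes.

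**Conclusion.** The point holds as a modest efficiency improvement. The primary test is valid and has 80.2% power at 3,250 per arm. Adjusting for baseline variables already recorded would raise this to about 81% to 85%, for assumed C-statistics of about 0.64 to 0.80. The direction is well founded. The size cannot be derived from the protocol and could be under one point.

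The figures assume the protocol's event rates, complete outcomes, and covariates that together reach the stated C-statistic in this restricted population.

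**What to change.** Before any unblinded look, including the interim analysis at 2,000 patients with one-year follow-up, amend section 13 so that:

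- the primary analysis is a logistic regression with randomised group, centre, age, ASA status (3 or 4), updated Charlson score and baseline WHODAS, with the list and functional forms fixed in advance;
- the treatment effect is reported as a standardised (marginal) risk difference and risk ratio with confidence intervals and tested at 0.049, which keeps the question about risk in the two groups and avoids relying on a conditional odds ratio;
- the centre-stratified Mantel-Haenszel test is kept as the supporting analysis.

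Two short rules are needed: how to fill in missing baseline values (WHODAS is the likeliest gap, as it depends on the patient's own report), and how to handle centres with very few or no deaths.

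The cost is some wording and a slightly more complex analysis. No extra patients or data collection are needed.

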- 10. WHODAS score: pre-operative, day 30 and 1 year
- 11. **Disability free survival**: disability-free survival up to 1 year: survival and freedom from new-onset disability, the latter defined as a 4-point reduction in the WHODAS score [56]. Disability in the WHODAS score is self reported by the participant, if the participant is unable to complete the score, then we will use a proxy's report as per WHODAS standard procedures. The date of onset of new disability will be recorded.
- 12. **Persistent post-operative pain**: pain over the surgical site, for at least three months after surgery, that cannot be explained by other causes, such as disease recurrence or a pre-existing pain syndrome.
- 13. **Cancer recurrence:** defined as clinical radiological or pathological evidence for recurrence of the tumour either at the local or a distant site.

Inclusion criteria

Age ≥ 60 years, ASA physical status 3 or 4, surgery expected to last ≥ 2 hours, post-operative hospital stay expected to be ≥ 2 nights, general anaesthesia with or without major regional block, able to monitor BIS throughout anaesthesia.

Exclusion criteria

Unable to monitor BIS (e.g. cranial or intracranial surgery), unable to consent, surgery with 'wake-up' test, propofol infusion for part or all of maintenance of anaesthesia ('total intravenous anaesthesia'), previous enrolment in Balanced study.

Intervention

General anaesthesia monitored with BIS. BIS targets will be either 50 or 35. We expect 90% of anaesthesia time to be within 5 units of the target BIS value and no deviations for >5 minutes.

Consent

Patients who are eligible for the trial will be given the patient information sheet by a member of the research team and encouraged to discuss the study with their family (or family/whanau in New Zealand) before written informed consent is sought, in accordance with local practice.

Treatment allocation

Once all entry details are recorded and eligibility confirmed, randomisation will be performed by contacting the automated on-line randomisation service with back-up phone service. Assignment to one of the two groups will be stratified by collaborating centre and a unique study number assigned. Investigators and research staff involved in patient followup are blinded to treatment allocation.

Perioperative Care

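### Adverse-event occurrence counts are to be compared by Poisson regression, or by a test chosen on incidence, with no stated allowance for repeat events clustering within patients (minor)

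*Protocol*

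**What the plan says.** Under Adverse events, section 13 has events that are not outcomes summarised by arm in two ways, as the share of patients affected and "as frequencies (number of occurrences) and compared between groups using Chi-square, Fisher's exact and Poisson regression depending on incidence rates". It does not say which test goes with which summary. It mentions no dispersion term, robust variance or handling of repeat events, and it sets no significance level for these comparisons.

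Three other places fix the scope:

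- Section 13, Secondary outcomes, compares the presence of each event (MI, cardiac arrest, stroke, PE, sepsis, surgical site infection, awareness, persistent pain). That is one yes/no per patient.
- Section 10, Recordings, collects at days 1 to 3 "Incidence of MI, cardiac arrest, PE, stroke, sepsis, surgical site infection and other adverse events". Other adverse events appear again at day 30 but are not in the one-year list.
- Section 10, Inclusion criteria, describes the population: "Age ≥ 60 years, ASA physical status 3 or 4, surgery expected to last ≥ 2 hours".

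**The concern.** Of the three named methods, only Poisson regression is built for occurrence counts. Its rate-ratio estimate is sound when events cluster, but its default standard error assumes that the variance of the count per patient equals the mean. In patients aged 60 or over, ASA 3 or 4, having varied major surgery, underlying risk will probably differ between patients and one patient may have several events. The variance would then exceed the mean, and the default standard error would be too small. A chi-square or Fisher's test on occurrence totals has the same fault, because it treats occurrences rather than patients as independent units.

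At stake is a nominally significant difference in adverse-event rates between the two depths of anaesthesia that reflects only how events bunch within patients.

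**Working it through.** **Inputs from the protocol.** "A power analysis using p1=0.10 and p2=0.08" "indicates that N=3250 patients are required in each group, β =0.8, α =0.049" (section 13, Power analysis). The 0.8 is read as power. The only figure carried forward from this is 3,250 patients per arm.

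**Reproducing the stated size.** Two-sided, pooled variance under the null, no continuity correction, mean proportion 0.09:

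n = [1.969 × √(2 × 0.09 × 0.91) + 0.842 × √(0.10 × 0.90 + 0.08 × 0.92)]² / 0.02² ≈ 3,233 per arm.

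The plan states 3,250, which gives power 0.802. The figure is reproduced.

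**Inputs assumed.** The protocol gives no rate or dispersion for non-outcome adverse events and no significance level for them. I take a two-sided 5% test, a mean of μ events per patient, and gamma-distributed patient risk. The count per patient then has variance μ + kμ² and variance-to-mean ratio φ = 1 + kμ.

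**Formula.** With event totals A and B in equal arms, the Poisson test is z = log(A/B) / √(1/A + 1/B). If the variance is φ times the mean, z has standard deviation √φ when there is no true difference, so

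rejection rate = 2 × [1 − Φ(1.96/√φ)].

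| φ | 1.96/√φ | Rejection rate at nominal 5% |
|---|---|---|
| 1.0 | 1.960 | 5.0% |
| 1.1 | 1.869 | 6.2% |
| 1.25 | 1.753 | 8.0% |
| 1.5 | 1.600 | 11.0% |
| 2.0 | 1.386 | 16.6% |

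The rate doubles to 10% at φ = (1.96/1.645)² = 1.42. On the log scale a correct interval is √φ times as wide: 12% wider at 1.25 and 41% wider at 2.

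**Simulation check.** 3,250 per arm, equal true rates, 20,000 runs per setting, model-based Poisson variance:

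| Mean events per patient (μ) | k = 1 | k = 2 | k = 5 |
|---|---|---|---|
| 0.01 | 4.8% | 5.0% | 5.4% |
| 0.05 | 5.5% | 6.1% | 7.9% |
| 0.1 | 5.9% | 7.5% | 11.2% |
| 0.3 | 8.6% | 11.8% | 21.5% |
| 1.0 | 16.8% | 25.8% | 42.4% |

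These agree with the formula. The distortion grows with kμ, so it is negligible for rare events and matters only for common, repeating or pooled ones.

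**Does the remedy work?** A separate 1,000 runs at μ = 0.3 (simulation error about 0.7 percentage points at 5%):

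| k | Model-based Poisson | Robust Poisson | Chi-square on patients with any event |
|---|---|---|---|
| 0 | 4.6% | 4.6% | 5.1% |
| 2 | 12.6% | 5.7% | 5.8% |
| 5 | 19.8% | 5.4% | 5.7% |

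**A loose anchor.** The nearest figure in the protocol is the pilot's one-month composite (section 9, Table 4): 19 of 61 and 11 of 62 patients, or 30/123 ≈ 24%. It mixes conditions that are not outcomes in the main trial (cardiac failure, DVT, pneumonia) with three that are (MI, PE, stroke). Suppose all non-outcome events pooled had a similar patient-level incidence. In the gamma-Poisson model φ = (1 − 0.244)^(−k), which is 1.15, 1.32 and 1.75 for k = 0.5, 1 and 2. The rejection rates are 6.8%, 8.8% and 13.8%. This is an illustration, not an estimate.

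**The case against.** The strongest reply is that the protocol names a family of methods and not a variance estimator. Poisson regression with robust standard errors already fits its wording, and such a choice is commonly left to the analysis plan, which is not at hand. This stands: the fault is possible under the text, not fixed by it.

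It is also fair to say that chi-square and Fisher's test pair naturally with the percentage of patients, so their misuse on occurrence totals is not planned. That stands too. Still, the only selection rule the sentence gives is the incidence rate, and that rule does not separate the two summaries. A robust variance for the Poisson model would not cure this part.

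A reader might go further and infer three things that the documents do not support:

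- *That Poisson regression tests the wrong null hypothesis.* It does not. Equal rates is the right hypothesis; the independence assumption sits in the model-based variance.
- *That the adverse-event intervals will be too narrow.* The protocol gives neither a variance estimator nor event rates, so this can only be said conditionally. For rare single events there is next to no effect.
- *That the trial's safety conclusions are at risk.* The paragraph covers non-outcome events only. The major harms, including awareness, are secondary outcomes compared as present or absent. The safety and quality hypotheses in section 8 concern early quality of recovery and awareness. The formal interim analysis in section 18 uses the primary outcome, and no adverse-event p-value triggers an action.

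Finally, the percentage of patients is reported alongside the counts, so a count difference driven by a few patients could be noticed.

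**Conclusion.** The point holds as a minor one. The sentence plans a between-arm comparison that includes occurrence counts, names one count method, and chooses among tests by incidence. If it is applied with the default Poisson variance, or with chi-square or Fisher's test on occurrence totals, standard errors will be too small whenever repeat events cluster in patients.

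At 3,250 per arm and a nominal two-sided 5%, the false-positive rate is about 5% for rare single events, about 8% at a variance-to-mean ratio of 1.25 and about 17% at a ratio of 2. These ratios are assumptions. The primary outcome, the secondary outcomes and the patient-level percentages are unaffected.

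**What to change.** Replace the comparison clause in section 13, Adverse events, with wording such as: *The number of patients with at least one event will be compared between groups by chi-square or Fisher's exact test, depending on expected cell frequencies. The number of occurrences per patient will be compared by Poisson regression with robust (sandwich) standard errors, or by negative binomial regression, with the patient as the unit of analysis.* If an analysis plan exists and already says this, a cross-reference is enough.

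The cost is one or two sentences and a software option. No new data are needed beyond the occurrence counts, kept by patient. The downside is somewhat wider intervals for event-rate ratios where events cluster.
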